Estimates from the literature were used to calculate the sample size needed for this study for the outcomes of changes from month 0 to month 5 in our primary outcome, heart failure quality-of-life. We assumed that the standard deviations (SD) seen in the current study would be similar to that in a similar study conducted in an urban setting in the United States.¹³ Sample size calculation were based assuming 80% power for a two-sided test at alpha of 0.05, and SD of 20.0. With the outcome of change in heart failure quality of life score from baseline to 5 months, considering as a minimum clinical difference of 10 points in the heart failure quality of life score, the sample size

needed was 63 individuals in each arm. We assumed a retention in the current study of 80%, thus the sample size needed at recruitment was at least 158 (n=79 in each arm)

8) Framework

The superiority hypothesis testing framework will be used, testing whether exposure to the intervention results in better outcomes than exposure to the control standard of care. Comparisons will be presented as differences between arms in changes in outcomes from baseline to 1 month to capture changes in acute heart failure symptoms and 30-day readmission; and from baseline to 5 months of follow-up to capture longer term and potentially sustained benefits.

9) Statistical interim analyses and stopping guidance

- a. Information in interim analyses specifying what interim analyses will be carried out and listing time points
 - i. None planned
- b. Any planned adjustment of the significance level due to interim analysis
 - i. No
- c. Details of guidelines for stopping the trial early
 - i. None

10) Timing of final analyses

Final analyses will begin in Fall 2021 upon completion of all field data collection in Fall 2020 and completion of all medical record data collection (Summer 2021).

11) Timing of outcome assessments

Research staff administered full surveys to both arms at baseline, 1 month, and 5 months. Additional brief surveys were collected at months 2 and 3. Medical record data were collected continuously in both arms from 3 months prior to baseline until 9 months after baseline.

Section 4: Statistical Principles

12) Level of statistical significance

95% confidence intervals and exact p-values (or $p<0.001$) will be reported.

13) Description and rationale for any adjustment for multiplicity and, if so, detailing how the type I error is to be controlled.

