- b. Unable to be contacted: 16 intervention participants were randomized but were not able to be contacted by POH to start the intervention and were considered as early withdrawals. Control participants could not be excluded as "early withdrawals" because the next visit would be a month after the baseline. Therefore, researchers modified the protocol and made a phone call to the control participants, right after the randomization, to simulate the call that the intervention participants had by POH to be enrolled in the food and nutrition program. From among control participants called right after randomization in the modified protocol, 2 could not be reached and were considered early withdrawals.

The number of participants with major and minor protocol deviations will be summarized by study arm.

16) Analysis populations – definition of analysis populations, e.g. intention to treat, per protocol, complete case, safety

- a. Intent to treat - The primary analysis will be intent to treat (ITT). The ITT analysis will include all participants in both arms who were randomized, completed all baseline assessments, and who had at least one follow-up visit. (see CONSORT).
- b. Adjusted intention to treat analysis. To adjust for early withdrawals, a propensity score for receiving the intervention will be developed and used to estimate the probability of each participant to receive the intervention. The adjusted ITT analysis will be performed adjusting for the propensity score and for baseline covariates that were different between arms.
- c. Per protocol - The per protocol analysis will include all participants in the ITT sample with baseline and follow-up evaluations and who adhered to the food and nutrition intervention. The minimal adherence will be considered as receiving at least 50% of weeks food and groceries, and at least 1 visit with the dietitian. This definition may be

revised depending on the distribution of adherence in the intervention participants. See appendix 1 for details about the food and nutrition education intervention.

- d. Complete case— We will not conduct complete case analyses as we will attempt to use all available data from all participants.

Section 5: Trial Population

17) Screening Data –

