- a. Participants were recruited through reviewing patient lists of hospitalizations in collaboration with providers in the Family Medicine and Cardiology Departments at San Francisco General Hospital. At provider meetings, research staff presented study details and eligibility guidelines.
- b. Screening was conducted in two stages, during an initial review of medical charts and at a visit with a participant while they were in the hospital prior to discharge. During the medical chart screening, potential participants were screened for congestive heart failure exacerbation diagnosis during their current hospital admission, age 18 years or older, language English or Spanish, less than 6 admissions to ZSFG in the last 12 months, no end stage renal disease diagnosis or known plan to initiate dialysis within 6 months, no severe aortic stenosis diagnosis, no mention of life expectancy less than 1 year, no cognitive impairment, currently housed, discharge plan for patient to discharge home, and currently living in San Francisco. Participants who met all criteria then proceeded to the in-hospital screening, which included confirming potential participants are housed and living in San Francisco, are not receiving more than 7 meal per week of food support, do not have any disqualifying allergies to commonly used foods used at POH, have a refrigerator and freezer to store food and are able to reheat and prepare meals and snacks at home, are able to eat by themselves or have assistance to eat, have cognitive capacity to consent to be in a research study, and are not moving in the next 6 months to a housing situation that does not meet study eligibility criteria.
- c. A summary will be provided indicating the number of participants screened, number of participants eligible, non-eligible and reason for non-eligibility, number of participants enrolled, number of participants eligible but not enrolled and reason, and number of participants randomized.

18) Eligibility – summary of eligibility criteria

Criteria for inclusion of subjects:

1. Adults hospitalized at ZSFG with acute decompensated heart failure/congestive heart failure exacerbation
2. Adults with their primary residence within San Francisco
3. Age: >18 years old
4. Languages: English or Spanish
5. Housed at a location where they would be able to securely receive, store and reheat food

Criteria for exclusion of subjects

1. Patients with severe or critical aortic stenosis.

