2. Patients with six or more hospital admissions within the last twelve months
3. Patients who are being discharged to a living facility that provides meals to residents.

4. Patients who anticipate moving from their current housing situation to one that does not meet our inclusion criteria within six months of enrollment.
5. Patients who are part of meal provision program that provides more than 7 meals a week to the patient.
6. Patients who are unable to feed themselves and do not have adequate support to help them with feeding.
7. Patients with limited physical, cognitive, or behavioral abilities that would interfere with their ability to follow-up with a study as determined by their ability to receive the Project Open Hand services and follow up with survey interviews
8. Patients with anticipated life expectancy of less than a year.
9. Patients who lack capacity to consent to a research study.
10. Patients currently requiring dialysis or determined to need dialysis in the next 6 months.
11. Patients with severe allergies to eggs, soy, wheat, nuts, seeds, seed oils, pineapple, raisins, or certain vegetables such as onions (allergies are considered on a case-by-case basis in consultation with Project Open Hand).

19) **Recruitment** – A CONSORT flow diagram will be used to summarize the number of participants who were:

- a. Assessed for eligibility at screening
 - i. Among people with heart failure, 2996 people were assessed for eligibility
 1. 2451 did not meet the inclusion criteria
 2. 127 Discharged before doing the baseline evaluations
 3. 226 were not interested in participating in the study
 - ii. Eligible and randomized
 1. 192 were eligible and randomized
 - a. 106 allocated in the intervention arm
 - i. 27 were early withdrawals
 - b. 86 allocated in the control arm
 - i. 4 were early withdrawals

See CONSORT diagram for detail on reasons for ineligibility

20) Withdrawal/follow-up

Reasons and details of withdrawal and lost to follow up at month 1 and 5 for both arms will be reported and summarized in the CONSORT flow diagram.

- a. Level of withdrawal, e.g., from intervention and/or from follow-up
 - i. Participants were withdrawn from the study due to unavailability to immediately reach out by phone, not meeting the eligibility criteria or deceased immediately following the randomization.

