- i. Hospitalization and Emergency Department use: As a secondary Aim 1 outcome, self-reported data as well as abstracted medical record data on hospital readmission and Emergency Department use were collected. From the data we will assess the number of times participants were admitted to the hospital from baseline to 1 month and from baseline to five months and the cumulative probability of being hospitalized by study arm. The following outcomes will be reported:

1. Admissions to Zuckerberg San Francisco General Hospital from baseline to 1 month, as determined by medical records. Number of admissions to Zuckerberg San Francisco General Hospital from baseline to 1 month, by study arm, adjusting for baseline values (-3 to 0 months).
2. Admissions to Zuckerberg San Francisco General Hospital from baseline to 5 months, as determined by medical records. Number of admissions to Zuckerberg San Francisco General Hospital from baseline to 5 months, by study arm, adjusting for baseline values (-3 to 0 months).
3. Admissions to any hospital from baseline to 1 month, as determined by ZSFGH medical records and self-report of admission to hospitals other than ZSFGH. Number of admissions to any hospital from baseline to 1 month, by study arm, adjusting for baseline values (-3 to 0 months).
4. Admissions to any hospital from baseline to 5 month, as determined by ZSFGH medical records and self-report of admission to hospitals other

than ZSFGH. Number of admissions to any hospital from baseline to 5 months, by study arm, adjusting for baseline values (-3 to 0 months).

- a. Cumulative probability to be admitted to any hospital from baseline to 5 months by study arm.
- 5. Emergency room utilization at Zuckerberg San Francisco General Hospital from baseline to 1 month, as determined by medical records. Number of admissions to the emergency room at Zuckerberg San Francisco General Hospital from baseline to 1 month, by study arm, adjusting for baseline values (-3 to 0 months).
- 6. Emergency room utilization at Zuckerberg San Francisco General Hospital from baseline to 5 months, as determined by medical records. Number of admissions to the emergency room at Zuckerberg San Francisco General Hospital from baseline to 5 months, by study arm, adjusting for baseline values (-3 to 0 months).

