Appendix 1: Description of the intervention components

i. Medically tailored meals and groceries:

The five-month intervention followed a tapered model: participants received 100% daily nutrition during the first and second months following discharge from the hospital, 66% daily nutrition during the third month, and 33% daily nutrition during the fourth and fifth months. The intervention was designed to provide easy-to-prepare food during the first 30 days post-discharge and to gradually incorporate items requiring more preparation over the course of the study period. All food was delivered directly to participants' homes, unless they requested pick-up instead. The tapered medically-tailored meal (MTM) plan is summarized in Figure A1.1 and described below:

- a. **Month 1** (30 days, twice weekly deliveries): participants received two frozen medically tailored meals per day and supplies for daily breakfasts, including items such as milk, oats, cereal, yogurt, and fruit.
- b. **Month 2** (30 days, twice weekly deliveries): participants received one frozen medically tailored meal per day; supplies for daily breakfasts, as described above; and groceries equivalent to one meal per day. Each grocery bag contained 2 protein choices, $\frac{1}{2}$ dozen eggs, 2 dairy choices, 6 raw produce options, 2 bean options, and 3 grain options.
- c. **Month 3** (30 days, one weekly delivery): participants received one frozen medically tailored meal per day and groceries equivalent to one meal per day, as described above.
- d. **Month 4** (30 days, one weekly delivery): participants made the choice to receive either one frozen medically-tailored meal per day **or** groceries equivalent to one meal per day, as described above.
- e. **Month 5** (30 days, one weekly delivery): participants received groceries equivalent to one meal per day, as described above.

Figure A1.1 - Visual Overview of Tapered MTM Intervention

Month 1	Month 2	Month 3	Month 4	Month 5
 Daily breakfast   supplies 14 frozen meals/wk	 Daily breakfast  supplies  (7 meals/wk)	 Groceries  (7 meals/wk)	 Groceries (7 meals/wk)  OR 7 frozen meals/wk	 Groceries (7 meals/wk)

	7 frozen meals/wk			
--	-------------------	--	--	--

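### The 1-month admission and ED counts start at a pre-discharge baseline, so as written they are not the 30-day readmission that item 8 says they capture

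*Combined protocol and SAP*

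**What the plan says.** Two clocks run through the document.

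**Baseline clock.** Item 22b.i, outcome 1, is "Number of admissions to Zuckerberg San Francisco General Hospital from baseline to 1 month, by study arm"; outcome 5 is the matching ED count. All eight outcomes in that list, the cumulative probability under outcome 4 and the 9-month counts in item 22d.i start at baseline. The counts are adjusted for utilization in the three months before it. Item 11 sets record abstraction on the same clock: "Medical record data were collected continuously in both arms from 3 months prior to baseline until 9 months after baseline". Item 15 places the first follow-up visit there too: "the next visit would be a month after the baseline".

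**Discharge clock.** The trial design (item 5) starts the food upon discharge and the control arm's meals in the sixth month after discharge. Appendix 1 counts food months and dietitian visits from discharge, for example "The intervention was designed to provide easy-to-prepare food during the first 30 days post-discharge".

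**Where baseline falls.** Item 17 has the in-person screening take place "at a visit with a participant while they were in the hospital prior to discharge". Item 19 lists "127 Discharged before doing the baseline evaluations" among the people not randomized.

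**Purpose of the 1-month window.** Item 8 says outcomes are compared "from baseline to 1 month to capture changes in acute heart failure symptoms and 30-day readmission", and gives the 5-month comparison the longer-term, possibly sustained, benefit.

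**The concern.** A 30-day readmission count needs 30 days at risk after the index discharge. If the clock starts while the patient is still in hospital, the days before discharge can contain neither a readmission nor programme food. The same number of days then drops off the end of the post-discharge month. The count is lower than the quantity named in item 8, by an amount that varies with each patient's remaining stay.

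Two matters follow from the same text. First, with baseline inside the index stay, the index admission and the ED visit that may have led to it fall in the pre-baseline covariate window, and the plan does not say whether they are counted. Second, the 5-month count contains the first month. A benefit confined to that month would show in the 5-month result and could be read as the longer-term effect.

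**Working it through.** **1. Does baseline precede discharge?** The item 19 flow closes: 2451 + 127 + 226 + 192 = 2996. The 127 are therefore a separate group lost because discharge came before baseline. With in-hospital screening, this places the baseline of those randomized before discharge. It is a strong inference: no passage dates baseline. Item 22d.i treats 9 months from baseline as four months after a five-month intervention (5 + 4 = 9), as if the two clocks coincided.

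**2. Plan figures to reproduce.** There are none for utilization. The only sample size is for KCCQ: 2 × (1.96 + 0.84)² × 20² / 10² gives 63 per arm, and 63 / 0.80 gives 79 per arm, 158 in all. Both reproduce, and neither bears on this point.

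**3. Time at risk lost.** Let g be the days from baseline to discharge. The documents do not give g; 0 to 7 is assumed. The share of a window of W days spent before discharge is g/W. For risk, assume a true 30-day readmission risk p of 25% and a constant hazard h = -ln(1 - p)/30. The risk captured is 1 - exp(-h(30 - g)).

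| g (days) | g/30 | g/150 | g/270 | captured risk |
|---|---|---|---|---|
| 0 | 0% | 0% | 0% | 25.0% |
| 1 | 3.3% | 0.7% | 0.4% | 24.3% |
| 3 | 10.0% | 2.0% | 1.1% | 22.8% |
| 5 | 16.7% | 3.3% | 1.9% | 21.3% |
| 7 | 23.3% | 4.7% | 2.6% | 19.8% |

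At g = 7, an assumed risk of 15% becomes 11.7%, and 30% becomes 23.9%.

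**4. Effect on the comparison.** With constant rates a and b in the two arms and the same g, the counts are a(30 - g) and b(30 - g). Their ratio stays a/b. The absolute difference shrinks by (30 - g)/30, which is 23/30 = 0.77 at 7 days. With the 79 and 82 participants in item 20, an assumed control risk of 25% and an assumed hazard ratio of 0.5, power to compare the two proportions is 46% at g = 0, 43% at g = 3 and 38% at g = 7.

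**5. Overlap of the windows.** Assume 0.25 admissions per control in month 1, 0.10 per month afterwards, and a 40% cut in month 1 only. The control total is 0.25 + 4 × 0.10 = 0.65. The intervention total is 0.15 + 0.40 = 0.55. The ratio is 0.846, a 15% fall over five months, although the count after month 1 is 0.40 in both arms.

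**6. Are the data there?** With g = 7, day 150 after discharge is day 157 after baseline, well inside the 9-month (about 270-day) abstraction.

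**The case against.** The gap is not in the documents. Losing people to discharge before baseline also fits baselines done late in the stay, with a gap near zero. This stands: the defect is in the rule as written, and its size is unknown.

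The term 30-day readmission appears only as rationale in item 8. Aim 1 speaks of fewer hospitalizations and ED visits, and no outcome in item 22b.i uses the term. This also stands. A reader might infer that a stated trial objective goes unmeasured, but the documents support only a mismatch between one rationale and the counting rule.

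A reader might also infer that the counts are biased toward an arm. The gap reflects the index stay and should be similar in the arms as randomized, so the documents do not support that.

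The cumulative 5-month count is a legitimate total effect: in the example above, 0.65 to 0.55 is a real reduction. Mean admissions after month 1 can be approximated by subtraction. Both points are fair, but subtraction gives no planned estimate or interval for the later period to which item 8 refers.

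Re-anchoring has limits. The any-hospital outcomes use self-report, and no passage says those events carry dates. Some visits fell outside a window of one month either way, an error that could exceed a few days' gap. Discharge does not remove all time without intervention either, since the first dietitian visit may come up to 14 days later.

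**Conclusion.** The concern holds for the 1-month ZSFGH counts. They start at a baseline done before discharge and do not give the 30-day post-discharge readmission named in item 8. The loss is 3.3% of the window per day of gap: 3% to 23% for an assumed 1 to 7 days, and nothing if baseline was done on the day of discharge. These shares apply to event counts under a constant rate. If admissions are concentrated soon after discharge, the loss is smaller, because the days cut off are the last ones.

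It does not follow that all utilization windows are materially wrong: for 7 days the loss is at most 4.7% at 5 months and 2.6% at 9 months. The consequence is lower counts and less precision in both arms alike, on secondary outcomes of a pilot. The KCCQ sample size is unaffected. The correction is still worth making, because it is cheap and leaves the 1-month result meaning what item 8 says.

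**What to change.** - **Outcomes 1 and 5 of item 22b.i:** count ZSFGH admissions and ED visits over days 0-30 after the index discharge date. Keep the from-baseline count, which stays closer to randomization, as a supporting analysis.
- **Index admission:** state that it and its ED visit are handled identically for all patients in the pre-baseline covariate and are excluded from the follow-up count.
- **Reporting:** give days from baseline to discharge, and any deaths before discharge, by arm. This shows the true size of the problem and checks that it is alike in the arms.
- **Longer-term effect:** add a ZSFGH count for days 31-150 after discharge beside the cumulative 5-month count.
- **Any-hospital outcomes:** re-anchor only where self-reported events are dated. Otherwise keep the baseline anchor and do not call the count 30-day readmission. State the time origin of the log-rank and Kaplan-Meier analysis on the same principle.

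The cost is SAP wording and a re-cut of ZSFGH records already abstracted, which include the index stay. The downside is that discharge can fall after randomization, so the rare patient not discharged alive needs a stated analysis rule.
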